## **Background and Significance:**

Dual antiplatelet therapy consisting of aspirin and an ADP P2Y12 receptor antagonist is the cornerstone of treatment for the prevention of thrombotic events in patients with acute coronary syndrome (ACS), including patients with ST-segment elevation myocardial infarction (STEMI) undergoing primary percutaneous coronary intervention (PPCI) [1-3]. The new-generation P2Y12 receptor inhibitors prasugrel and ticagrelor are associated with more prompt and potent platelet inhibition, and better clinical outcomes than clopidogrel in ACS patients [4]. Therefore, prasugrel and ticagrelor are considered the first choice in this setting [1-4]. However, in STEMI patients undergoing PPCI there is a delayed onset of action of oral P2Y12 receptor inhibitors, including prasugrel and ticagrelor, which require more than 2 hours to exert their full antiplatelet effects, and thus exposing these high-risk patients to an increased risk of early thrombotic complications [5-8]. The mechanism of this delayed onset of antiplatelet effect is likely multifactorial due to the presence in the setting of STEMI of specific conditions that translate into delayed drug absorption which in turn affect the pharmacokinetic (PK) and pharmacodynamic (PD) profiles of oral P2Y12 receptor inhibitors [5-8]. Crushing prasugrel and ticagrelor improves their PK and PD profiles as it favors drug absorption and onset of antiplatelet effects and because of this, it is commonly used in STEMI patients undergoing PPCI [9,10]. However, despite the use of crushed tablets, up to one-third of patients may still have high on-treatment platelet reactivity (HPR) within the first 2 hours after loading dose (LD) administration of these oral agents [9,10]. These findings support the need for intravenous agents with more rapid platelet inhibiting effects.

Cangrelor is a potent intravenous P2Y12 receptor inhibitor with rapid onset and offset of action associated with a greater reduction in ischemic events, including stent thrombosis,

compared with clopidogrel in P2Y12 receptor naïve patients undergoing PCI (including stable coronary artery disease, non-STE-ACS and STEMI) [4,11,12]. To date most studies have explored cangrelor in the setting of PCI subjects treated with clopidogrel and the clinical profile of cangrelor among patients treated with prasugrel or ticagrelor is currently unknown. This is noteworthy because ACS patients, in particular STEMI undergoing PPCI, are commonly treated with either prasugrel or ticagrelor. Moreover, cangrelor is also more likely to be used in these higher risk settings. PD investigations conducted *in vitro* or *ex vivo* in stable patients have shown cangrelor to be associated with enhanced platelet inhibition compared with that induced by prasugrel and ticagrelor [13-15]. However, the PD effects of cangrelor in STEMI patients undergoing PPCI treated with a newer generation P2Y12 receptor inhibitor and how this compares with a crushed formulation of the oral drug is unexplored. Because of a potential for drug-drug interactions with thienopyridines, drug regulating authorities only recommend that ticagrelor, and not prasugrel, be administered concomitantly with cangrelor [16-18]. Accordingly, ticagrelor is being chosen to test our study hypothesis in this investigation and will be administered as a crushed formulation as this has shown to be associated with fastest onset of effects of an oral formulation agent.

### **Study Aim**

The aim of this prospective randomized study is to investigate the PD effects of cangrelor in STEMI patients undergoing PPCI treated with crushed ticagrelor.

## **Research plan**

[figure not shown]
### ***Research Design***

The proposed investigation is a prospective, randomized, double-blind, parallel design PD study. This study will be performed at the University of Florida Health Jacksonville - Division of Cardiology. Patients will be recruited and consented at the Emergency Department or Catheterization Laboratory of our Institution. Patients will be screened by cardiology research staff, who will verify that all candidates meet inclusion criteria. After providing written informed consent, STEMI patients undergoing PPCI will be eligible for randomization. After diagnostic angiography and prior to commencement of the PCI procedure, patients will be randomly assigned 1:1 to receive either cangrelor (30 µg/kg bolus followed by 4 µg/kg/min infusion) or matching placebo (normal saline bolus and infusion). The bolus will be administered at the same time of a 180mg crushed ticagrelor LD and infusion will be continued for 2 h. The 180-mg LD of ticagrelor will consist in 2 ticagrelor 90-mg tablets that will be crushed using a commercially available syringe crusher. After, 5 rotations of the crushing mechanism, 25mL water will be aspirated into the syringe and mixed by shaking for 30 seconds. This suspension will be dispensed into a 165mL dosing cup. The syringe crusher will be rinsed using additional 25 mL water, which will be added to the dosing cup for a total of 50mL suspension administered orally to patient. Patients will be administered the ticagrelor LD in the cardiac catheterization laboratory after diagnostic angiography and before starting PPCI (before passing the wire through the target lesion).

All patients will be treated as per local standard of care, which includes 325 mg aspirin LD and 4000 IU of unfractionated heparin at time of presentation. The choice of intravenous anticoagulant during PPCI (heparin or bivalirudin) will be at discretion of the physician

performing PPCI. After PCI, all patients will receive aspirin 81 mg/d indefinitely and ticagrelor 90 mg bid for at least 12 months. The PCI procedure will be performed as per local practice standards, including the route of access (femoral vs. radial), use of aspirations device, and stent type. Patients receiving glycoprotein IIb/IIIa inhibitors before the primary end point time point will be excluded due to their interference with the VerifyNow assay.

PD assessment will be performed at the following 8 time points: baseline (before LD administration), 5 minutes, 30 minutes, 1 hour, and 2 hours after bolus, at the end of PCI (when the guide catheter was removed at procedure completion), and 1 hour and 2 hours after stopping the infusion. A flow diagram of the study is presented below.

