#### *Exclusion criteria:*

- Inability to provide written informed consent
- Known history of prior intracranial bleeding

- On treatment with a P2Y12 receptor antagonist (ticlopidine, clopidogrel, prasugrel, ticagrelor) in the prior 10 days
- Known allergies to aspirin, ticagrelor or cangrelor
- On treatment with oral anticoagulant
- Treatment with glycoprotein IIb/IIIa inhibitors before the primary end point time point
- Fibrinolytics within 24 hours
- Active bleeding
- High risk of bleeding
- Known platelet count  $<80 \times 10^6/\text{mL}$
- Known hemoglobin  $<10 \text{ g/dL}$
- Intubated patients (prior to randomization)
- Known creatinine clearance  $<30 \text{ mL/minute}$  or on hemodialysis.
- Known severe hepatic dysfunction
- Patients with sick sinus syndrome (SSS) or high degree AV block without pacemaker protection
- Current treatment with drugs interfering with CYP3A4 metabolism (to avoid interaction with ticagrelor): Ketoconazole, itraconazole, voriconazole, clarithromycin, nefazodone, ritonavir, saquinavir, nelfinavir, indinavir, atazanavir, and telithromizycin.
- Pregnant or lactating females.

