#### *Blood sampling and Laboratory assessments*

Blood samples (10 mL) will be drawn through the arterial access sheet used for the PCI procedure for time points (until the end of PCI) while patient are in the cath lab; post-cath lab samples will be drawn through venous sampling. Samples will be collected in anticoagulated and serum tubes at each study time point for all PD assessments. The first 2-4 mL of blood will be discarded to avoid spontaneous platelet activation.

Laboratory assessments will include 2 PD assays:

1. VerifyNow PRU assay
2. VASP-PRI assay

*Description of laboratory assays*

*1) VerifyNow PRU:* The VerifyNow System is a turbidimetric based optical detection system which measures platelet induced aggregation as an increase in light transmittance (Accumetrics, San Diego, CA) and will be utilized according to manufacturer's instructions, as previously described [5]. The assay is based on microbead agglutination and uses specific reagents for the pathways of interest. The VerifyNow PRU assay, by combining ADP+PGE1, measures changes in platelet function specific to P2Y12 receptor inhibitors. The assay is based upon the ability of activated platelets to bind fibrinogen. Fibrinogen-coated microparticles aggregate in proportion to the number of GP IIb/IIIa receptors expressed. Microbead aggregation is more rapid and reproducible if platelets are activated; therefore the reagents are incorporated into the assay channel to induce platelet activation without fibrin formation. Light transmittance increases as activated platelets bind and aggregate fibrinogen-coated beads. The instrument measures this change in optical signal and reports results in P2Y12 Reaction Units (PRU).

*2) Whole blood vasodilator-stimulated phosphoprotein (VASP):* VASP phosphorylation (VASP-PRI) is a marker of P2Y12 receptor reactivity, which is the target for ticagrelor. VASP will be assessed according to standard protocol using labeled monoclonal antibodies by flow cytometry with the Platelet VASP-FCM kit (Biocytex Inc., Marseille, France) as previously described [5]. PGE1 increases VASP-P levels by stimulation of adenylate cyclase. Binding of ADP to P2Y12 leads to Gi-coupled inhibition of adenylate cyclase. Therefore, the addition of ADP to PGE1-

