### **Sample Size Computation, Power Analysis and Statistical Analysis**

Assuming a common standard deviation of 70 PRU, a sample size of 20 patients per group will allow to detect a 70 PRU difference between groups (~160 PRU with ticagrelor vs ~90 PRU with ticagrelor plus cangrelor) with 85% power and a two-sided  $\alpha = 0.05$ . Considering the 2 arms and a possible ~25% rate of invalid results due to hemolysis, technical problems, or drop-out, we plan to randomize up to 50 patients, in order to have complete data for the primary

end point analysis. Our sample size is based on data derived from previously published studies [10,20,21].

The PD population will include all patients with PD data and without a major protocol deviation thought to affect significantly the PD of ticagrelor or cangrelor. The PD population will be used for analysis of all primary and secondary PD variables. Erroneously treated patients (e.g., those randomized to one treatment but actually given the other) will be accounted for based on the actual treatment received.

Categorical variables will be expressed as frequencies and percentages. Continuous variables will be presented as mean  $\pm$  SD or median [IQR]. Continuous variables will be analyzed for normal distribution with the Kolmogorov-Smirnov test. Comparisons between categorical variables will be performed using two-tailed Fisher's exact test or the Pearson's chi-square test. Student's t test, Mann-Whitney U-test and Wilcoxon test will be used to compare continuous variables when appropriate. An analysis of covariance will be used to evaluate the primary end point and all between-group comparisons in platelet reactivity. A mixed linear model will be used to evaluate the overall difference between groups over time and within-group comparisons. A p value  $<0.05$  will be considered statistically significant for superiority analyses. Statistical analysis will be performed using a SPSSv22.0 software (SPSS Inc. Chicago, IL).

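### The GP IIb/IIIa inhibitor exclusion removes whole randomised patients for a VerifyNow-only reason, then stops at 30 minutes and leaves later affected PRU values in the secondary analyses

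*Combined protocol and SAP*

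**What the plan says.** Five parts of the combined protocol and SAP bear on this.

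- **Research Design, the rule:** "Patients receiving glycoprotein IIb/IIIa inhibitors before the primary end point time point will be excluded due to their interference with the VerifyNow assay". The unit removed is the patient, and assay interference is the only reason given.
- **Exclusion criteria:** the same condition appears among the eligibility criteria: "Treatment with glycoprotein IIb/IIIa inhibitors before the primary end point time point".
- **Research Design, timing and blinding:** "After diagnostic angiography and prior to commencement of the PCI procedure, patients will be randomly assigned 1:1". The study is double-blind with matching placebo. The samples are listed as "PD assessment will be performed at the following 8 time points: baseline (before LD administration), 5 minutes, 30 minutes, 1 hour", followed by 2 hours after the bolus, end of PCI, and 1 and 2 hours after the infusion stops.
- **Primary and secondary objectives:** the primary end point is PRU 30 minutes after the loading dose and bolus. Secondary objectives are PRU at the other time points, PRI at all time points, and HPR rates at all time points (PRU above 208 or PRI above 50%).
- **Sample Size Computation, Power Analysis and Statistical Analysis:** the PD population is "all patients with PD data and without a major protocol deviation thought to affect significantly the PD of ticagrelor or cangrelor", and "The PD population will be used for analysis of all primary and secondary PD variables". Inhibitor use is not mentioned there.

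**The concern.** An eligibility criterion should be decidable at randomisation. This one stays open until 30 minutes after the bolus, so it can remove a patient who has already been randomised and dosed.

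The reason given does not justify removing the whole patient. It concerns VerifyNow, whose readout the protocol links to the receptor: "Fibrinogen-coated microparticles aggregate in proportion to the number of GP IIb/IIIa receptors expressed". It does not cover PRU drawn before the inhibitor. Nor does it mention VASP-PRI, which the protocol describes as flow cytometry of VASP phosphorylation, with no GP IIb/IIIa step.

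The cut-off does not follow from the reason either. If the inhibitor disturbs VerifyNow at 20 minutes, it does so at 90 minutes. By inference from the assay description, blockade would lower PRU and could hide HPR. Such values would enter the later PRU comparisons, PRU-based HPR and the mixed model unflagged.

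At stake are the make-up of the PRI data set and the reliability of PRU after 30 minutes. Both feed secondary objectives.

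**Working it through.** **The plan's own figure.** The plan gives no figure for inhibitor use. Its sample-size figure is sound on its own terms. With a difference of 70 PRU, SD 70, 20 per group and two-sided alpha 0.05, the standardised difference is 70/70 = 1. Power is then 86.9% by two-sample t test and 88.5% by normal approximation, against a stated 85%. This point does not alter that calculation.

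**Inputs.** There are 8 time points and 2 assays, so 8 × 2 = 16 planned results per patient. The infusion lasts 2 hours, so the two post-infusion samples fall at 3 and 4 hours after the bolus. Fixed samples after the bolus are therefore at 5 and 30 minutes and at 1, 2, 3 and 4 hours. The end-of-PCI sample floats.

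**Use after the bolus and before 30 minutes: results removed that the stated reason does not cover.** All PRI is counted here, on the inference that the VASP assay is unaffected.

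| First use | PRI | PRU drawn earlier | Total of 16 |
|---|---|---|---|
| Bolus to 5 min | 8 | 1 (baseline) | at least 9 (56%) |
| 5 to 30 min | 8 | 2 (baseline, 5 min) | at least 10 (63%) |

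The totals say at least because the end-of-PCI sample might also precede the inhibitor.

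**First use after 30 minutes: PRU exposed to interference but kept.**

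| First use | Later fixed samples | With end of PCI, if later |
|---|---|---|
| 30 min to 1 h | 1, 2, 3, 4 h = 4 of 8 | 5 of 8 |
| 1 to 2 h | 2, 3, 4 h = 3 of 8 | 4 of 8 |

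**Trial-wide scale, on assumed rates.** Suppose 1, 3 or 5 of 50 randomised patients are excluded under the rule, and all samples are otherwise obtained. The PRI results lost are 8, 24 or 40 of 50 × 8 = 400, or 2%, 6% or 10%. Complete data is also an assumption, since the plan itself allows for about 25% invalid results.

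The precision regained is slight. Adding one patient to one arm of 20 changes the standard error by the factor √[(1/21 + 1/20)/(2/20)] = √0.976 = 0.988, a reduction of about 1.2%.

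**The texts side by side.** Take a patient first given the inhibitor at 20 minutes. Research Design and the exclusion list remove the patient. The PD population definition asks whether a major deviation affected the PD of ticagrelor or cangrelor. Assay interference is not such an effect, so on its own terms that definition does not remove the patient. For a patient first given it at 90 minutes, neither text says what happens to the later PRU.

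**Primary end point.** On the protocol's own account of interference, a 30-minute PRU drawn after the inhibitor cannot be used. It is lost whether the patient or only the sample is removed, so the primary data set is the same.

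**The case against.** The strongest defence is that Research Design and the exclusion list give one explicit rule, and the PD population is a general definition that applies to whoever remains. Using one common set of patients for PRU, PRI and HPR is also a defensible choice in a 50-patient PD study. A reader might go further and infer that the sections flatly contradict each other. The text does not support that: they can be read in sequence, and a reader could class inhibitor use as a major deviation because it is a listed exclusion. What remains is a mismatch between the stated reason and the PD population criterion. The sequential reading still drops PRI data for a VerifyNow reason and still leaves PRU after 30 minutes without a rule.

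A second objection is that the documents nowhere say PRI is valid after a GP IIb/IIIa inhibitor. That stands. Validity is inferred from the assay description and needs laboratory confirmation.

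A third is that the size rests on assumed rates and complete data, and that results count as discarded only if sampling would have continued. This also stands. The per-patient counts follow from the schedule; the trial-wide percentages only show scale.

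A reader might also infer that the rule biases or underpowers the primary comparison. The documents do not support this either. They give no rate of inhibitor use and no link between use and platelet reactivity, and blinding with matching placebo limits unequal use, though it cannot rule it out. Any bias from these missing values is of unknown size and direction. Any power lost through unusable 30-minute values would be lost under sample-level handling too.

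**Conclusion.** The point holds as one about secondary data handling, and it should be corrected. The rule extends an eligibility criterion past randomisation, removes more than its reason covers, does not line up with the PD population definition, and stops at a time point unrelated to the interference it cites.

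For an affected patient the share is substantial: more than half of planned results removed with early use, or 3 to 5 of 8 PRU values left exposed with first use between 30 minutes and 2 hours. Across the trial the effect may be small, because the number of affected patients is unknown. The case for keeping PRI depends on the VASP assay being unaffected; the gap after 30 minutes does not.

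**What to change.** 1. In Exclusion criteria and Research Design, limit the eligibility criterion to inhibitor use before randomisation.
2. For use after randomisation, set to missing only the PRU and PRU-based HPR values drawn after the inhibitor, at any time point, including after 30 minutes.
3. Keep earlier PRU. Keep PRI and PRI-based HPR provided the laboratory confirms that the VASP assay is unaffected. State both in the PD population definition so that the three sections agree.
4. Report inhibitor use by arm and by timing (before or after 30 minutes), with the number of patients in each PRU and PRI analysis.

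The cost is wording in three sections and one small table, with no new assay or time point. Affected patients continue to be sampled, and PRU and PRI analyses will have different numbers of patients, so the single common analysis set is lost. A sensitivity analysis for missing 30-minute PRU is optional. The change concerns data handling only and says nothing about when an inhibitor may be given.

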### ***Study Population***

#### *Inclusion criteria:*

- Patients with STEMI undergoing primary PPCI
- Age > 18 years old

#### *Exclusion criteria:*

- Inability to provide written informed consent
- Known history of prior intracranial bleeding

- On treatment with a P2Y12 receptor antagonist (ticlopidine, clopidogrel, prasugrel, ticagrelor) in the prior 10 days
- Known allergies to aspirin, ticagrelor or cangrelor
- On treatment with oral anticoagulant
- Treatment with glycoprotein IIb/IIIa inhibitors before the primary end point time point
- Fibrinolytics within 24 hours
- Active bleeding
- High risk of bleeding
- Known platelet count  $<80 \times 10^6/\text{mL}$
- Known hemoglobin  $<10 \text{ g/dL}$
- Intubated patients (prior to randomization)
- Known creatinine clearance  $<30 \text{ mL/minute}$  or on hemodialysis.
- Known severe hepatic dysfunction
- Patients with sick sinus syndrome (SSS) or high degree AV block without pacemaker protection
- Current treatment with drugs interfering with CYP3A4 metabolism (to avoid interaction with ticagrelor): Ketoconazole, itraconazole, voriconazole, clarithromycin, nefazodone, ritonavir, saquinavir, nelfinavir, indinavir, atazanavir, and telithromizycin.
- Pregnant or lactating females.

#### *Blood sampling and Laboratory assessments*

Blood samples (10 mL) will be drawn through the arterial access sheet used for the PCI procedure for time points (until the end of PCI) while patient are in the cath lab; post-cath lab samples will be drawn through venous sampling. Samples will be collected in anticoagulated and serum tubes at each study time point for all PD assessments. The first 2-4 mL of blood will be discarded to avoid spontaneous platelet activation.

Laboratory assessments will include 2 PD assays:

1. VerifyNow PRU assay
2. VASP-PRI assay

*Description of laboratory assays*

*1) VerifyNow PRU:* The VerifyNow System is a turbidimetric based optical detection system which measures platelet induced aggregation as an increase in light transmittance (Accumetrics, San Diego, CA) and will be utilized according to manufacturer's instructions, as previously described [5]. The assay is based on microbead agglutination and uses specific reagents for the pathways of interest. The VerifyNow PRU assay, by combining ADP+PGE1, measures changes in platelet function specific to P2Y12 receptor inhibitors. The assay is based upon the ability of activated platelets to bind fibrinogen. Fibrinogen-coated microparticles aggregate in proportion to the number of GP IIb/IIIa receptors expressed. Microbead aggregation is more rapid and reproducible if platelets are activated; therefore the reagents are incorporated into the assay channel to induce platelet activation without fibrin formation. Light transmittance increases as activated platelets bind and aggregate fibrinogen-coated beads. The instrument measures this change in optical signal and reports results in P2Y12 Reaction Units (PRU).

*2) Whole blood vasodilator-stimulated phosphoprotein (VASP):* VASP phosphorylation (VASP-PRI) is a marker of P2Y12 receptor reactivity, which is the target for ticagrelor. VASP will be assessed according to standard protocol using labeled monoclonal antibodies by flow cytometry with the Platelet VASP-FCM kit (Biocytex Inc., Marseille, France) as previously described [5]. PGE1 increases VASP-P levels by stimulation of adenylate cyclase. Binding of ADP to P2Y12 leads to Gi-coupled inhibition of adenylate cyclase. Therefore, the addition of ADP to PGE1-

stimulated platelets reduces PGE1-induced VASP-P levels. If P2Y12 receptors are successfully inhibited by ticagrelor or cangrelor, addition of ADP will not reduce the PGE1-stimulated VASP-P levels. The platelet reactivity ratio (PRI) will be calculated after measuring VASP-P levels after stimulation with PGE1 (MFI PGE1) and also PGE1 + ADP (MFI PGE1 + ADP). The P2Y12 reactivity ratio =  $([MFI\ PGE1] - [MFI\ PGE1 + ADP]/[MFI\ PGE1]) \times 100\%.$

